9.2.2 Representativeness

The recall of the performed SLR is considered as representative for the population of pregnant women using corticosteroids in early pregnancy or first trimester. The conclusions out of this research are expected to be as close as possible to a representative sample of these women.

Cleft palate, even being one of the most common congenital malformations, is too rare to conduct studies with an optimal representative sample. Furthermore, the ethical aspects of conducting interventional clinical trials in pregnant women to investigate the occurrence of congenital malformations in the offspring following drug exposure limit the availability of research in the area. Therefore it is justified to conduct this study in order to answer the research question.

9.3 Variables

9.3.1 Exposure definition

The primary exposure of interest is glucocorticoid use.

• First trimester exposure: At least one prescription for glucocorticosteroids redeemed from the first day of the last menstrual period to the end of gestational week 12

OR

• Early pregnancy: At least one prescription for glucocorticosteroids redeemed from 30 days before estimated conception to the end of the first trimester

Our primary comparison group includes women not using glucocorticoid during pregnancy.

9.3.2 Outcomes definition

The primary outcome variable is the incidence of any type of orofacial cleft. Oral clefts are defined as diagnosis of cleft lip with or without cleft palate or isolated cleft palate.

Please refer to section 4 of systematic literature review report provided in Appendix 1 for the detailed scope of the research.

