9.2.1 Selection criteria used for the Systematic Literature Review (SLR)

The inclusion and exclusion criteria used for the selection of studies as well as detailed methodology of the systematic literature review are provided in the Appendix 1.

No time period restriction was used. The systematic literature review was conducted to identify all studies (including observational studies and clinical trials) published till 25 June 2018 (search date). In addition, there were no restrictions to the route of administration.

Only 18 studies were shortlisted based on the inclusion criteria. All of the 18 studies were observational studies while no clinical trials were identified that met the inclusion criteria.

The selection criteria utilized in the SLR were the following:

Inclusion criteria

- Population: Pregnant women
- Intervention: Any glucocorticoid or corticosteroid or steroids use irrespective of mode of administration
- Comparator: Any/none
- Outcomes: Incidence/ risk of cleft lip/palate in infants
- Study Design:
 - Meta-analysis and systematic literature reviews
 - Observational studies (such as cohort study, case-control study, registries data)
 - Clinical trials Phase IIb, III, and IV
 - Conference abstracts/posters
- Time period: No time period restriction
- Geography: No geography restriction

Exclusion criteria

- Population: Nonpregnant women
- Intervention: Drugs other than glucocorticoid or corticosteroid or steroid
- Outcomes: Incidence/ risk of cleft lip/palate in infants
- Study Design:
 - Animal Study

- In vitro studies
- o Editorial, letters, comment
- Clinical trials Phase I or preclinical
- Case reports, case series
- o Reviews
- Studies focusing on:
 - Diagnosis and surgical procedure for cleft repair
 - o Impact of Increased internal corticosteroids due to stress
 - The relationship between genetic mutations and cleft patients
 - Adverse events for other drugs
 - Safety profiles of glucocorticoid or corticosteroid

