9.7 Data analysis

- Direct treatment comparison: Any glucocorticoid or corticosteroid or steroids use irrespective of mode of administration vs. no use of glucocorticosteroids
- Model: Fixed effect model will be used. We assume that the underlying effect size is the same across the studies. The differences in observed effects are only due to random error or sampling error within the studies. The observed effects mainly depend on the sample size and weighted average mean might give a precise estimation of the overall effect. However, any deviation from this assumption will be discussed.
- Measure of relative effect: For the dichotomous outcomes will be assessed by Odds ratio (OR). Given that the event of our interest is a rare outcome, we assume relative risk (RR) equivalent to OR.
- Inverse variance method: Studies with less variance or standard deviation are given more weight. The variance of weighted average can be minimized through this method and hence inverse variance method will be used to assess the direct treatment effect
- Effect size is assessed by Odds ratio (OR) as it is a rare outcome
- Publication bias: Reporting or publication bias will be assessed by using the funnel plot (symmetry or asymmetry) and it again confirmed by using the Egger's test (in case of asymmetry funnel plot). Further, any outliers in the effect size will be determined by Galbraith plot
- Sensitivity analysis: In order to know the robustness of the findings, sensitivity analysis will be performed with and without outlier studies so that any uncertainty can be determined. This will be done only in case of high level of heterogeneity observed. However, plausible reasons for high heterogeneity (unexplained variation) will be discussed in the MAR
- Sub-group analyses will be performed for
 - Route of administration:
 - Topical
 - Systemic
 - Any other form of use
 - Types of orofacial cleft
 - Cleft lip (CP)
 - Cleft lip with or without palate (CLP)
 - Cleft palate (CP)
 - Orofacial cleft (OC)
 - Potency of glucocorticoid
 - Mild
 - Moderate
 - Potent
 - Very potent
- 95% credibility intervals will be used as a measure for the expression of the difference (overlap / no overlap with 1 for OR)
- Data will be analysed by using the metafor package in R software version 3.5.1

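### The primary outcome does not separate clefts due to chromosomal or single-gene syndromes, so a true association could be pulled towards 1 and by different amounts across studies

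*Protocol*

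**What the plan says.** Protocol section 9.3.2 states: "The primary outcome variable is the incidence of any type of orofacial cleft". It then gives the case definition: "Oral clefts are defined as diagnosis of cleft lip with or without cleft palate or isolated cleft palate". For anything further it sends the reader elsewhere: "Please refer to section 4 of systematic literature review report provided in Appendix 1 for the detailed scope of the research". That report is not among the documents at hand.

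The selection criteria in section 9.2.1 are equally broad: "Outcomes: Incidence/ risk of cleft lip/palate in infants". The covariates (9.3.3), the subgroups and sensitivity analysis (9.7) and the limitations (9.9) do not mention syndromic status.

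On the model, section 9.7 says: "We assume that the underlying effect size is the same across the studies". It attributes differences between observed effects to sampling error alone, and adds that departures from this assumption will be discussed. Its sensitivity analysis removes outlier studies, and only if heterogeneity is high.

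**The concern.** The protocol asks whether exposure in early pregnancy disturbs the formation of the lip and palate, which section 7 places between weeks 4 and 12. A cleft that belongs to a chromosomal or single-gene syndrome has a cause that is in place before that window. Counting it as an outcome event adds cases that carry no information about exposure.

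Two things are at stake:

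- **Bias towards no effect.** If exposure does raise the risk of other clefts, the added cases shrink the OR. For a safety study requested by a health authority, this is the direction that can hide a signal.
- **Differences between studies.** The analysis pools published estimates, so each study's own case definition applies. If some of the 18 studies left out syndromic cases and others did not, their ORs would differ even with the same true effect.

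The protocol's wording also affects extraction. Where a paper gives one estimate for all clefts and another without syndromic cases, 9.3.2 as written points to the all-cleft figure.

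**Working it through.** The protocol gives no figure on this point, so there is none to reproduce. What can be checked is the direction and the possible size of the effect.

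**Inputs**

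- Baseline cleft rate: 1 in 700 births (section 7).
- True OR: section 7 says that some studies report a 3- to 6-fold increase and others find none. The values 1, 1.5, 2, 3 and 6 cover this range.
- s, the share of cases among the unexposed that is syndromic and unrelated to exposure: not in the documents. Assumed to be 5% to 30%.

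**Formula**

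Let p be the baseline risk. In the unexposed it splits into s x p (syndromic) and (1 - s) x p (other). Exposure multiplies only the second part. For a rare outcome, where section 9.7 treats the relative risk and the OR as equal, this gives

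observed OR = [s x p + (1 - s) x p x true OR] / p = (1 - s) x true OR + s.

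An exact calculation at p = 1/700 agrees with this formula to within 0.002 over the values used here.

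**Results**

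| True OR | s = 5% | s = 10% | s = 20% | s = 30% |
|---|---|---|---|---|
| 1 | 1.00 | 1.00 | 1.00 | 1.00 |
| 1.5 | 1.475 | 1.45 | 1.40 | 1.35 |
| 2 | 1.95 | 1.90 | 1.80 | 1.70 |
| 3 | 2.90 | 2.80 | 2.60 | 2.40 |
| 6 | 5.75 | 5.50 | 5.00 | 4.50 |

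Worked example: 0.7 x 3 + 0.3 = 2.40. The formula also gives observed OR - 1 = (1 - s) x (true OR - 1), so the excess over 1 shrinks by exactly the share s. With no true effect there is no distortion.

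**Gap between two studies with the same true effect**

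Compare a study that excludes syndromic cases with one that includes them, on the log OR scale used for inverse-variance pooling:

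- true OR 3, s = 30%: ln(3/2.40) = 0.22
- true OR 1.5, s = 30%: ln(1.5/1.35) = 0.11
- true OR 3, s = 5%: ln(3/2.90) = 0.03
- true OR 1.5, s = 5%: ln(1.5/1.475) = 0.02

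The gap therefore runs from negligible to material, depending on two quantities that the documents do not fix.

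**The case against.** The strongest objection is that no dilution has been shown. The case mix was set by the 18 source studies, which are not at hand. If they excluded syndromic cases, or if the true OR is 1, nothing is lost. Section 4 of the literature review report may restrict the outcome, and the statistical analysis plan, also not shown, may hold extraction rules. Every figure above rests on an assumed s, and 0.22 comes from its upper end. Section 9.7 already promises to discuss departures from the common-effect assumption.

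Most of this stands, and it makes the point conditional. It does not remove it. The ENCePP checklist (item 6.2) names 9.3.2 as the place where the outcome is defined, and that section says that every type of cleft counts. An extraction rule elsewhere that preferred non-syndromic estimates would depart from this wording. A promise to discuss heterogeneity does not ensure that case definitions are recorded, and dropping outliers does not separate studies by case definition.

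Two stronger readings are tempting, and the documents support neither:

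- A reader might infer that the word isolated, attached only to cleft palate in 9.3.2, removes syndromic cases from that type and leaves them in the lip group. But the protocol uses the word anatomically: section 7 speaks of isolated cleft lip as a diagnosis alongside cleft lip and palate, and the abstract and section 9.7 list plain cleft palate. On that reading the wording does not create unequal counting rules.
- A reader might infer that the protocol contradicts itself, because 9.2.1 excludes studies focusing on "The relationship between genetic mutations and cleft patients". That line screens out papers by topic. It says nothing about cases within the included studies.

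**Conclusion.** The point holds in a conditional form. The visible protocol defines the primary outcome as all orofacial clefts and has no rule for clefts attributed to a chromosomal or known single-gene syndrome. If included studies counted such cases and the true OR exceeds 1, the pooled OR is biased towards 1. Over an assumed share of 5% to 30%, the excess over 1 falls by that same 5% to 30%. If studies handled such cases differently, their ORs would also differ by up to about 0.22 on the log scale at a true OR of 3.

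This rests on three assumptions: that syndromic cases are unaffected by exposure, that at least some source studies counted them, and that the unseen review report does not already restrict the outcome. The documents do not show that dilution has occurred or how large it is. The change is still worth making, because it is cheap and the planned sensitivity analysis does not cover the issue.

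**What to change.** In section 9.3.2, add that where a study reports an estimate excluding clefts attributed to a chromosomal or known single-gene syndrome, that estimate is extracted for the pool, with the same rule for every cleft type. If the review report already restricts the outcome in this way, say so in 9.3.2.

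In the data extraction table (9.6), record for each of the 18 studies whether such cases were excluded, included or not described.

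In section 9.7, add a sensitivity pool limited to the studies that excluded them, run whatever the observed heterogeneity.

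The cost is a sentence in 9.3.2, one extraction column and one more pooled result. There are two limits. The main pool still mixes case definitions wherever a study gives only an all-cleft estimate, so the restricted pool is the one that addresses the mixing. That pool will contain fewer studies and be less precise.

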9.3.3 Covariate definition

Covariates of interest for this meta-analysis are:

- Potency of glucocorticoids
- Route of administration

9.4 Data sources

Embase and Medline via Ovid®, Cochrane database, Google Scholar have been used for data collection as described in Appendix 1.All records retrieved from the literature searches have been screened for relevancy based on eligibility criteria (inclusion/exclusion). Relevant back references from the shortlisted studies have also been reviewed.

Screening steps:

First level: screening based on title/abstracts

All the records retrieved from the literature search (using multi-string search strategy) were screened based on the title and abstract supplied with each citation. Each citation was screened by two independent reviewers, and any discrepancies between reviewers were reconciled by a third independent reviewer. Citations that do not match the eligibility criteria were excluded at this stage; whereas unclear citations were included. Duplicates of citations (due to overlap in the coverage of the databases) were excluded.

Second level: screening of full text

The eligibility criteria were applied to the full-text citations. Each full-text were screened by two independent reviewers, and any discrepancies between reviewers were reconciled through a third independent reviewer. Studies included after this stage were included for the next step i.e. data extraction.

Extraction of relevant data

Data from included studies was extracted by one reviewer and the quality of the data was checked by the second reviewer, with reconciliation of any differences by a third independent reviewer.

9.5 Study size / Recall

18 observational studies were selected for meta-analysis by predefined eligibility criteria. For details, please refer to section 4 of systematic literature review report provided in Appendix 1.

9.6 Data management

The evidence for the present meta-analysis was gathered through secondary research on the published studies and meta-analyses. We considered quantitative data from the research. Based on the evidence identified from SLR, risk association of orofacial cleft and glucocorticoids exposure during pregnancy was assessed by the odds ratios (ORs) with corresponding 95% credibility intervals (CIs). As this is a rare outcome, the odds ratio will be used as an approximation of the relative risk. A detailed and comprehensive data extraction table in MS Excel will be created to capture the relevant information from the studies identified from systematic literature review. This will then be imported into the R software for meta-analyses.

9.7 Data analysis

- Direct treatment comparison: Any glucocorticoid or corticosteroid or steroids use irrespective of mode of administration vs. no use of glucocorticosteroids
- Model: Fixed effect model will be used. We assume that the underlying effect size is the same across the studies. The differences in observed effects are only due to random error or sampling error within the studies. The observed effects mainly depend on the sample size and weighted average mean might give a precise estimation of the overall effect. However, any deviation from this assumption will be discussed.
- Measure of relative effect: For the dichotomous outcomes will be assessed by Odds ratio (OR). Given that the event of our interest is a rare outcome, we assume relative risk (RR) equivalent to OR.
- Inverse variance method: Studies with less variance or standard deviation are given more weight. The variance of weighted average can be minimized through this method and hence inverse variance method will be used to assess the direct treatment effect
- Effect size is assessed by Odds ratio (OR) as it is a rare outcome
- Publication bias: Reporting or publication bias will be assessed by using the funnel plot (symmetry or asymmetry) and it again confirmed by using the Egger's test (in case of asymmetry funnel plot). Further, any outliers in the effect size will be determined by Galbraith plot
- Sensitivity analysis: In order to know the robustness of the findings, sensitivity analysis will be performed with and without outlier studies so that any uncertainty can be determined. This will be done only in case of high level of heterogeneity observed. However, plausible reasons for high heterogeneity (unexplained variation) will be discussed in the MAR
- Sub-group analyses will be performed for
 - Route of administration:
 - Topical
 - Systemic
 - Any other form of use
 - Types of orofacial cleft
 - Cleft lip (CP)
 - Cleft lip with or without palate (CLP)
 - Cleft palate (CP)
 - Orofacial cleft (OC)
 - Potency of glucocorticoid
 - Mild
 - Moderate
 - Potent
 - Very potent
- 95% credibility intervals will be used as a measure for the expression of the difference (overlap / no overlap with 1 for OR)
- Data will be analysed by using the metafor package in R software version 3.5.1

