Post Authorization Safety Study (PASS) Information

Acronym/Title	Risk association of orofacial cleft and G lu c oc o rti c oids exposure during pregnancy: a meta-analysis			
Protocol version and date	1.2, 16 November 2018			
IMPACT study number	20638			
Study type / Study phase	Observational, Meta-analysis of published literature			
EU PAS register number	TBD, Study not yet registered			
Active substance	Diflucortolone valerate (BAY 866146); Glucocorticoids (drug class: corticosteroids)			
Medicinal product	Nerisona			
Product reference	BAY 866146			
Procedure number	NA			
Comparator / Reference therapy	Unexposed control			
Study Initiator and Funder	Bayer AG			
Research question and objectives	A systematic literature review was conducted to identify evidence on the risk of development of cleft palate in neonates after glucocorticoids exposure during pregnancy. The published meta-analyses are outdated and have some shortcomings. Evidence gathered from systematic literature review is heterogeneous and does not answer the question. Thus, a meta-analysis of the evidence identified in the systematic literature review is warranted. The primary objective of this meta-analysis is to investigate the relationship between the exposure of glucocorticoids during pregnancy and orofacial cleft development. Secondary objectives are to perform subgroup analyses for: • Potency of glucocorticoid • Route of administration • Types of orofacial cleft			
Country(-ies) of study	NA			

Author

Marketing authorization holder

Marketing authorization holder(s)	Bayer AG
MAH contact person	

The study will be conducted in compliance with the protocol and any applicable regulatory requirements.

Throughout this document, symbols indicating proprietary names (®, TM) may not be displayed. Hence, the appearance of product names without these symbols does not imply that these names are not protected.

1. Table of contents

1.	Table of contents3	
2.	List of abbreviations	4
3.	Responsible parties	5
3.1	Study initiator and funder	5
4.	Abstract	6
5.	Amendments	9
6	Milestones	0
U.		
7.	Rationale and background	9
8.	Research questions and objectives	.11
8.1 0 2	Primary objective	.11
0.2	Secondary objective	.11
9 .	Research methods	.11
9.1	Study design	.11
9.2	Selection criteria used for the Systematic Literature Review (SLR)	12
9.2.	2 Representativeness	.12
9.3	Variables	.13
9.3.	1 Exposure definition	.13
9.3.	2 Outcomes definition	.13

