Population	Pregnant women exposed to any glucocorticoid or corticosteroid or steroids in early pregnancy or first trimester of pregnancy irrespective of mode of administration identified from articles published up to 25 June 2018 by pre-specified inclusion and exclusion criteria				
Variables	 Exposure definition First trimester exposure Early pregnancy Outcomes definition Oral clefts Cleft lip with or without palate Cleft palate Covariate definition Potency of glucocorticosteroids Route of administration of glucocorticosteroids 				
Data sources	 Embase and Medline via Ovid®, Cochrane database, Google Scholar has been used for data collection All records retrieved from the literature searches have been screened for relevancy based on eligibility criteria (inclusion/exclusion). Relevant back references from the shortlisted studies have also been reviewed. 				
Study size	18 observational studies have been selected for meta-analysis by predefined eligibility criteria in a previously conducted SLR.				
Data analysis	 Direct treatment comparison: Any glucocorticoid or corticosteroid or steroids use irrespective of mode of administration vs. no use of glucocorticosteroids Model: Fixed effect model Measure of relative effect: For the dichotomous outcomes will be assessed by Odds ratio (OR) Inverse variance method Effect size are assessed by Odds ratio (OR) as it is a rare outcome Publication bias: Using funnel plot, Egger's test, Galbraith plot Sensitivity analysis Sub-group analyses Route of administration: Types of orofacial cleft Potency of glucocorticoid 				

	 Data will be analysed by using the metafor package in R software version 3.5.1 The results of the outcomes will be described as eman with 95% credibility intervals (CI) and presented as Forrest plots 			
Milestones	Start of data collection (SLR): 12 June 2018			
	End of data collection (SLR): 25 June 2018			
	Final report (SLR): 9 July 2018			
	Meta-analysis protocol: 09 November 2018			
	Statistical analysis plan: 10 September 2018			
	Meta-analysis report: November 2018			

5. Amendments

Not applicable.

6. Milestones

Table 1 presents the planned milestones for the project. These milestones are based on a timely review and approval of the project. Administrative changes to milestones due to delays in study preparation, data release and analysis do not require amendments to the protocol.

Table 1: Milestones

Milestone	Planned date
Start of data collection (SLR)	12 June 2018

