Bayer's glucocorticoid product, Nerisona (INN) Diflucortolone valerate (for topical use) is contraindicated for use during pregnancy. In the scope of a regulatory procedure, the French Health Authority has requested Bayer to conduct a meta-analysis encompassing all studies investigating a possible increase in the risk of cleft palates in neonates of women treated with glucocorticoids during the first trimester of pregnancy.

In response to this request, a systematic literature review (SLR) was conducted to identify relevant studies evaluating the potential association between the exposure to glucocorticoids and the occurrence of orofacial cleft. Due to the heterogeneity findings in the 18 selected publications, a meta-analysis of their results was deemed as warranted and will be conducted as originally requested. Since this analysis will evaluate the risks of a medicinal product class used in a patient population for which safety information is limited or missing (e.g. pregnant women), it is considered as a Post Authorization Safety Study (PASS), in accordance with the European Medicine Agency Guideline on good pharmacovigilance practices (GVP) Module VIII – Post -authorisation safety studies (Rev 3) (18).

Of note, a meta-analysis for topical administration of corticosteroids during early pregnancy is not published. Nevertheless, a meta-analysis (16) was identified in the SLR that discusses effect of use of corticosteroids during early pregnancy without specifying the route of administration. This meta-analysis also has some shortcomings such as:

- Relationship between dosage and duration of medication were not examined in the included studies that could affect their results
- Confounding factors, such as race, maternal age, level of education, economic and social status, smoking, chances of repetitive enrollment of some patients in different studies were not addressed
- Dosage of glucocorticoid was not discussed
- Recall and publication bias due to retrospective design

Thus, further analyses are warranted to investigate a concrete association between the exposure to glucocorticoids and the developmental orofacial cleft. The current meta-analysis aims to also address some of the shortcoming of the existing meta-analysis such as the confounder effect by subgroup analyses. However, not all shortcomings will be addressed due to lack of data availability in the published literature.

8. Research questions and objectives

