9.2 Setting

Pregnant women exposed to any glucocorticoid or corticosteroid or steroids in early pregnancy or first trimester of pregnancy irrespective of mode of administration identified through a systematic review of articles published up to 25 June 2018 by pre-specified inclusion and exclusion criteria (see section 4 of SLR in see Appendix 1). In total 18 observational studies have been selected for this meta-analysis with sample size for individual studies ranging from 106 to 832,636 patients.

- Source: Embase and Medline via Ovid®, Cochrane database, Google Scholar
- *Population sampling strategy:* All records retrieved from the literature searches were screened for relevancy based on eligibility criteria (inclusion/exclusion). The results were initially screened by title and abstract, and the shortlisted results were further screened on full text. Relevant back references from the shortlisted studies have also been reviewed.

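### The only pooling model assumes one common odds ratio, although the protocol calls the evidence heterogeneous, so the primary interval omits any between-study variance

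*Protocol*

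**What the plan says.** Section 9.7 fixes the model and its assumption: "Fixed effect model will be used. We assume that the underlying effect size is the same across the studies". It continues: "The differences in observed effects are only due to random error or sampling error within the studies". Weights are inverse-variance: "Studies with less variance or standard deviation are given more weight". The Abstract lists the same choice: "Model: Fixed effect model". If the assumption fails, the stated response is: "However, any deviation from this assumption will be discussed".

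Section 9.7 has three further provisions that bear on heterogeneity:

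- a Galbraith plot to identify outliers;
- a sensitivity analysis with and without outlier studies, run only if heterogeneity is high, with plausible reasons for it discussed in the report;
- subgroup analyses by route, cleft type and potency.

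No random-effects analysis is named anywhere in the protocol, in either a primary or a sensitivity role.

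Elsewhere the protocol describes the evidence differently. The information table at the front says: "Evidence gathered from systematic literature review is heterogeneous and does not answer the question". Section 7 says: "Due to the heterogeneity findings in the 18 selected publications, a meta-analysis of their results was deemed as warranted". Section 9.9 names confounding, including the choice of treatment, as a possible explanation of clinical heterogeneity, and notes a wide range of doses.

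**The concern.** The feature that justifies the study is the one its primary model sets to zero. A common-effect interval reflects within-study sampling error only. When true odds ratios differ between studies, the uncertainty about their average has a second component, tau², which this interval leaves out. The error goes one way: the interval is too narrow for the average odds ratio whenever tau² is above zero.

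This matters because Section 9.7 expresses the result by whether the 95% interval overlaps an odds ratio of 1. An interval that is too short can appear to exclude 1, or to rule out a meaningful increase, on precision the data do not have. According to Section 7, the analysis answers a question from the French health authority about a class of medicines in early pregnancy, so overstated certainty in either direction is costly.

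**Working it through.** **Step 1. Is there a figure to reproduce?** No. The protocol gives no Q, I², tau², study-level odds ratio or standard error. The passages can be compared, but the arithmetic below is illustrative and rests on assumed inputs.

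**Step 2. The assumption against the rest of the protocol.**

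| Place | Content | Fits one common odds ratio? |
|---|---|---|
| 9.7, Model | Between-study differences are sampling error only | This is the assumption |
| Information table; Section 7 | Evidence is heterogeneous, and this motivates the pooling | No |
| 9.9 | Confounding and treatment choice may cause clinical heterogeneity; doses vary widely | No |
| 9.7, comparison | Any glucocorticoid by any route against none | Unlikely on its face |
| 9.3.1 | Two exposure windows accepted, one starting at the last menstrual period, the other 30 days before conception | Unlikely on its face |

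**Step 3. Do the planned safeguards repair the primary interval?** Discussing a deviation leaves the numbers as they are. Removing outliers gives a second estimate from fewer studies, and no other model is named for it. Subgroups give separate estimates, again with no other model named. None of these adds tau² to the primary interval.

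**Step 4. Size with equal study standard errors (assumed).** Let each of k studies have standard error s, and let I² = tau²/(tau² + s²).

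- Fixed-effect standard error: s/√k.
- True standard error of the same estimate: √(s² + tau²)/√k.
- Ratio of random-effects to fixed-effect width: 1/√(1 − I²), whatever the value of k.
- Coverage of the average by the fixed-effect interval: 2Φ(1.96 × √(1 − I²)) − 1.

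| I² | 1.96 × √(1 − I²) | Coverage | Width ratio |
|---|---|---|---|
| 0 | 1.96 | 95% | 1.00 |
| 25% | 1.70 | 91% | 1.15 |
| 50% | 1.39 | 83% | 1.41 |
| 75% | 0.98 | 67% | 2.00 |

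**Step 5. Size with unequal standard errors (assumed).** Take k = 18, the number of studies in Section 9.2, with standard errors of the log odds ratio log-spaced over a range and w = 1/s². The fixed-effect standard error is 1/√Σw. Its true value under heterogeneity is √(Σw²(s² + tau²))/Σw. The random-effects standard error with tau known is 1/√Σ(1/(s² + tau²)). Entries are fixed-effect coverage, with the width ratio in brackets.

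| Range of s | tau = 0 | tau = 0.1 | tau = 0.3 | tau = 0.5 |
|---|---|---|---|---|
| 0.2 to 0.6 | 95% (1.00) | 93% (1.07) | 80% (1.46) | 64% (1.98) |
| 0.1 to 0.8 | 95% (1.00) | 88% (1.23) | 57% (2.09) | 39% (3.01) |
| 0.05 to 1.0 | 95% (1.00) | 72% (1.65) | 32% (3.39) | 20% (5.07) |

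The loss is nil at tau = 0 and slight at small tau with similar standard errors. It grows with tau and with the spread of precision.

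**Step 6. Does the alternative behave?** In simulations of 18 studies with standard errors log-spaced from 0.15 to 0.90 (assumed), fixed-effect coverage was about 72% at tau = 0.3 and 53% at tau = 0.5. A random-effects model (Paule-Mandel tau²) with a Hartung-Knapp interval covered 93 to 94% in both cases, and about 95% at tau = 0.

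**The case against.** The strongest reply is that heterogeneity is reported only in words. Section 8 contrasts high with non-significant risks, but significance varies with study size even under one odds ratio. The contrast in Section 7 between 3- to 6-fold risks and no association is background literature, not stated to be the spread of the 18 studies, and it cites the earlier meta-analysis on both sides. This stands. A reader might infer that the interval will certainly be far too narrow, and the documents do not support that.

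Second, a reader might infer from Section 9.2 ("sample size for individual studies ranging from 106 to 832,636 patients") that one or two very large studies will decide the answer. That does not follow. For a rare outcome, precision depends chiefly on exposed cases rather than total size, and totals are not comparable between cohort and case-control studies. In the three patterns of Step 5 the most precise study carries 13%, 22% and 30% of the fixed-effect weight, purely as a result of the assumed standard errors. The actual weights are unknown.

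Third, it would be wrong to say that discussion is the only response planned. The outlier analysis and the subgroups exist and deserve credit, although Step 3 shows that they leave the primary interval unchanged. Section 7 presents the subgroups as a way to address confounding, so they should not be read as an admission that effects differ.

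Fourth, the ENCePP checklist in Annex 2 says that no hypothesis is tested, so overlap with 1 is not a formal decision rule. It is still the stated way of expressing the result.

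Fifth, an inverse-variance average can be defended as a summary of these 18 studies alone. Section 9.7 does not make that argument: it assumes a single underlying effect, and Section 9.2.2 aims at pregnant women using corticosteroids in general.

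Finally, random effects gives small studies more weight, and Section 9.9 anticipates recall and publication bias. It does not cure confounding either. This is a real cost and the reason to show both models.

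**Conclusion.** The point stands in conditional form. The protocol commits to a common-effect model as its only pooling model, and that assumption conflicts with its own account of the evidence. If true effects differ, the primary interval is too narrow for the average odds ratio, and nothing planned in this document corrects it.

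The contradiction and the direction of the error are firm. The size is not. It ranges from no loss at tau = 0 to severe undercoverage at high heterogeneity. The equal-standard-error figures are a plain guide: 83% coverage at I² = 50% and 67% at 75%. They and the unequal-standard-error figures rest on assumed inputs and are not predictions for these 18 studies. A correction is still warranted because it affects the primary result, and in the simulation little coverage was lost by using random effects when the common-effect assumption was true.

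**What to change.** In Section 9.7 and the Abstract:

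- Make a random-effects model primary, for example REML estimation of tau² with a Hartung-Knapp interval. Both are available in metafor, the package already chosen.
- Report tau² and I², and preferably a 95% prediction interval.
- Keep the inverse-variance fixed-effect result as a sensitivity analysis, shown beside the primary one.
- Delete the sentences in 9.7 that assume one common effect and attribute all differences to sampling error.
- Keep the outlier and subgroup analyses as additions, and align the SAP.

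The particular estimator is a reasonable choice among several. What matters is that the primary interval allows for between-study variance. The cost is wording in the protocol and SAP and a few model arguments. The interval will be wider if heterogeneity is present, and small studies will gain weight, so any gap between the two pooled estimates should be reported and discussed with the funnel plot.
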